At the time of surgery, adults will be admitted to the Neuroscience Patient Care Unit (NPCU). The patient will be asked to sign a standard surgical consent form that covers the tumor biopsy, microdialysis probe placement, and lumbar drain placement. These surgical procedures will be considered the beginning of Phase 1 of the trial for safety monitoring purposes. For the research surgical procedure, on study day 1, the stereotactic biopsy will be performed using frameless stereotaxy. A frozen section will be sent from the biopsy tissue. If the biopsy confirms recurrent tumor, the patient will continue with study procedures. If the biopsy is not consistent with recurrent tumor, the patient will not undergo further study procedures and will be replaced. The burrholes for the microdialysis catheters will be placed using stereotactic guidance in a similar fashion to the biopsy procedure. Lumbar drain placement will also be performed in this same surgical procedure. While the patient is under anesthesia, a hematology fellow may perform a bone marrow examination. Following biopsy and microdialysis catheter implantation, subjects will stay in the ICU for 24 hours, and then be moved to a private inpatient room with a one-on-one sitter until the time of resection, 7 days after the initial biopsy. The first dose of Nivolumab will be given at 48 hours after the biopsy on study day 3. The lumbar drain catheters will remain clamped in between CSF sampling to allow the patients to be mobile during their inpatient stay. A stereotactic CT scan will be performed after the biopsy and microdialysis catheter placement to verify accurate placement and assess for procedural complications. Phase 1 will end at the start of surgical resection of the tumor, and clinical care will then commence as outlined below. Primary outcome measures will be assessed at the conclusion of enrollment, as all samples will be sent for cytokine testing at that time. All patients will come for a safety monitoring visit 2 weeks after their second surgery (+/-1 week) for safety evaluation. All patients will continue with routine examinations and Nivolumab and BMS-986016

therapy every 2 weeks, starting on study Day 17 (+/- 2 days) until recurrence or a dose limiting toxicity is experienced with appropriate imaging.

4.5.2 Summary of Clinical Care Procedures and follow up (Study Phase 2):

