4.5.13 CSF Sample retrieval (Research)

CSF will be taken daily while the subject is in the ICU and during the patient's inpatient stay. The lumbar drain will remain clamped until the time of sampling. At that time, the first 5ml will be drained off to allow the clearance of debris and sediment, and then up to 15ml of CSF will be collected for studies and stored at -80 degrees C. On Day 3, additional samples of up to 10ml of CSF will be drawn (total for Day 3 up to 25ml of CSF). Up to 5ml will be withdrawn before, and 6 hours +/- 2 hours after the completion of the nivolumab dose for pharmacokinetic analysis. In the event that the lumbar drain fails and is not replaced, CSF collection will cease until the lumbar puncture performed in the operating room on Day 8. Up to 15ml will be withdrawn in the operating room during the lumbar puncture.

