7.17.1.2.2 Neurotoxicity

Given the toxicology studies showing choroid plexus inflammation in the setting of combination therapy, diligence regarding clinical monitoring of all subjects for signs and symptoms of neurologic toxicities was emphasized and should be maintained. In the early-phase studies, subjects with active neurological disease, as well as those with a confirmed history of encephalitis, meningitis, or uncontrolled seizures in the year prior to informed consent, have been excluded. As of the clinical data cutoff date of 15-Jul-2020, the observed drug-related AEs with potential for neurotoxic etiology have occurred at rates and with severity comparable to what would be expected with nivolumab monotherapy. The current relationab safety experience includes 10 (1 with monotherapy and 9 in combination with nivolumab) cases of aseptic meningitis (which is a rare IMAE with nivolumab monotherapy), neurotoxicity remains a specific IMAE of interest when combining relatlimab and nivolumab. The aseptic meningitis cases all presented with new or worsening headache with diagnosis made based upon increased immune cells found on CSF analysis in the absence of identifiable infectious etiology. Most cases responded to steroid therapy, 1 case responded without steroid therapy, and 1 case recurred during the steroid taper (responded to repeated high dose steroid treatment with taper). Two cases of encephalitis, Grade 3, have occurred with relatlimab in combination with nivolummab. No cases of myasthenia, demyelination or Guillain-Barre Syndrome have occurred. Refer to the specific treatment protocol for individual study-specific eligibility criteria; required procedures and instructions regarding neurotoxicity evaluation and monitoring as guidance may evolve with the increasing clinical and safety experience with combination of relatlimab and nivolumab.

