In addition to our standard post-operative care for our patients, we will be specifically assessing our patients for the following adverse events that are likely to be related to the research surgical procedure – intracerebral hemorrhage, meningitis and wound infection. Any grade of adverse events, as defined by CTCAE version 5.0, which occur within the first 3 patients will trigger an evaluation by the Safety Monitoring Committee to approve the enrollment of the next patient. Any adverse event Grade 2 or higher or any delay in planned surgery in any patient at any point during the pilot trial due to an adverse event related to the experimental procedures in Phase 1 will also trigger an evaluation by the Safety Monitoring Committee (for patients enrolled at NIH) and the Data and Safety Monitoring Board (for patients enrolled at the Emory Site) to approve the enrollment of the next patient.

Infusion reaction: Monitoring for an infusion reaction will begin on day 3 of the protocol within the patient's inpatient stay. This monitoring will consist of clinical observation, with q15 minute vital signs, during the infusion and for the first two hours after infusion. Specifically, we will be checking the patients for fever, chills, shaking, itching, rash, hypertension or hypotension or difficulty breathing during the administration of Nivolumab or immediately afterwards (within the subsequent 2 hours).

For infusion reactions, the patients will be treated according to I-O AE Algorithms from Appendices B and C; Investigator Brochures for Nivolumab (BMS-936558) and Relatlimab (BMS-986016). Generally, Grade 1 infusion reactions will be observed. Grade 2 or 3 infusion reactions will prompt interruption of the patient's infusion until the observed symptom returns to the level of a Grade 1 reaction. Patients will be given 25mg of Benadryl IV and 650 mg of Tylenol PO for any grade 2 or 3 infusion reaction. The Benadryl can be repeated once for symptom resolution until the reaction returns to a level of Grade 1. If a patient has a Grade 2 or 3 reaction, subsequent infusions will be preceded by 25mg of Benadryl IV and 650mg of Tylenol PO 30 minutes prior to dosing. Grade 4 reactions will cause discontinuation of the therapy.

Additionally, the following safety monitoring procedures will be undertaken during Phase 1 of the trial:

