-The patient will undergo an immediate post-operative neurological examination within 4 hours of the completion of the case to rule out any neurological morbidity after the research biopsy and microdialysis catheter placement;

-The patient's dressing will be examined on a daily basis for signs of infection including increased tenderness, foul odor, discharge or discoloration of the dressing.

-A CT scan will be performed in the immediate post-operative period within 8 hours of the completion of the case to ensure lack of hemorrhage at site of catheter implantation; -In the intensive care unit, the patient will undergo monitoring in the ICU for 24 hours after microdialysis catheterization, and then an inpatient stay with a one-on-one sitter (7 days) after biopsy

-The patient will have q2hr neurological checks for the first 24 hours after surgery -During the remainder of the patient's time while admitted, they will have q4hr neurological checks while awake;

-If any significant neurological changes are found on the neurological checks, the patient will be sent for a STAT head CT to rule out late onset of hemorrhage;

-Patient will have q4hr temperature checks while admitted

-Patient will be watched for signs and symptoms of adrenal insufficiency while admitted during nursing checks and daily physical exams

-Patients will have skin examinations and will be asked for signs and symptoms of immune-mediated rash while admitted

-CSF will be collected from the lumbar drain for safety monitoring on Mondays and Thursdays while the patient is in the inpatient unit, as long as the lumbar drain remains in place. We will send a cell count, protein, glucose, gram stain and culture from each sample

-Patients will undergo a CBC with differential daily while in the inpatient unit to watch for signs of infection.

-Patients will be monitored with metabolic panels daily during the microdialysis monitoring period

-Patients will undergo liver function testing on day 3 prior to study drug administration. -Patients will undergo CPK testing on day 3 prior to study drug administration.

Lab values that would preclude dosing of Nivolumab include:

-Creatinine > Upper limit of normal and > 1.5x baseline

-AST > 3.0 times upper limit of normal

-ALT > 3.0 times upper limit of normal

-Total bilirubin > 1.5 times upper limit of normal

-WBC > 2.0 times upper limit of normal

-CPK > 2.0 times upper limit of normal

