25.0 Study Calendar

	Before Surgery	Day 1	Qday Day 1	Day 3	Q6h Day 1 -	Day 8	Day 17 (+/- 2	Day 31 and every 2 wk. until	Survival Follow- up (approx monthly
			Day 8		Day 8		Days)	Progression	until
Informed consent	X							(+/- 2 Days)	death)
Demographics and Medical	1								
history	Х								
Physical exam									
(neuro exam, skin exam, vitals, weight, Karnofsky Status)*	X	Х	Х	Х		Х	Х	Х	
CT Head		Х							
Chest X-ray	Х								
Comprehensive metabolic			X						
panel (with creatinine)+ GGT	Х	Х	Λ	Х		Х	Х	Х	
TSH	Х			Х			Х	Х	
СРК				Х			Х	Х	
CRP				Х			Х	Х	
Free T3 and T4	Х						Х		
Liver function tests (including Tbili, AST and ALT)	Х			Х			Х	Х	
CBC with differential	Х	Х	Х	Х		Х	Х	Х	
Monitoring for infusion reaction and cytokine release syndrome				X			X		
QAC and QHS accuchecks			Х	Х					
ACTH and Cortisol**	Х						Х	Х	
MRI Brain with/without contrast	Х					Х	Х	X***	
Biopsy/microdialysis catheter placement		X							
Nivolumab administered				X			Х	X	
BMS-986016 antibody administered							Х	Х	
Research blood sample taken	Х	Х	Х	Х		Х	Х	Х	

PK Blood sample taken				X					
EKG and Troponin level****	Х						Х	Х	
Echocardiogram	Х						Х		
CSF sample taken****		Х	Х	Х		Х			
PK CSF sample taken				Х					
Microdialysis sample taken				Х	Х	Х			
Surgical resection/ Microdialysis catheter removal						X			
Bone marrow examination*****		X				Х			
Adverse event evaluation	Х	X	Х	X		X	Х	Х	
Telephone/Medical Record follow-up									Х

*Neurological exams will be conducted q2h for the first 24 hours after the research surgical procedure, then q4h while awake for the remainder of the microdialysis monitoring period

**Baseline ACTH and AM Cortisol levels will be obtained, and then further testing will be at the discretion of the treating physicians as clinically indicated

***MRI will be performed every other site visit in follow-up starting at day 17 (every 4 weeks)

****EKG and Troponin level will be taken before each of the first 5 doses of study drugs *****In addition to daily research samples, CSF will be collected qMonday and

Thursday for cell count, protein, glucose, gram stain and culture during inpatient stay as long as the lumbar drain remains in place

******Bone marrow examination is performed at the discretion of the PI

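### CSF cell counts are scheduled by weekday and not by study day, so a count before the Day 3 nivolumab dose is not guaranteed, which weakens attribution of a later pleocytosis

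*Combined protocol and SAP*

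**What the plan says.** Section 8.1.1 sets the safety sampling: "CSF will be collected from the lumbar drain for safety monitoring on Mondays and Thursdays while the patient is in the inpatient unit", for as long as the drain stays in. On each sample, "We will send a cell count, protein, glucose, gram stain and culture" are ordered. The footnote to the Study Calendar (25.0) gives the same rule: "In addition to daily research samples, CSF will be collected qMonday and" then "Thursday for cell count, protein, glucose, gram stain and culture during inpatient stay". Neither place ties a count to a study day or to the dose.

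The dose itself is tied to a study day. Section 4.5.1 says "The first dose of Nivolumab will be given at 48 hours after the biopsy on study day 3". Resection and drain removal follow on Day 8.

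Other CSF is drawn by study day. Section 4.5.13 provides daily research samples, stored frozen, and on Day 3 an extra draw: "Up to 5ml will be withdrawn before, and 6 hours +/- 2 hours after the completion of the nivolumab dose for pharmacokinetic analysis". No cell count is specified on any of this fluid.

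Two places show why CSF cells matter. Section 8.1.1 names the events to look for as likely results of the research surgery: "intracerebral hemorrhage, meningitis and wound infection". Section 7.17.1.2.2 describes the aseptic meningitis cases in the relatlimab programme, with "diagnosis made based upon increased immune cells found on CSF analysis in the absence of identifiable infectious etiology". Section 8.2 requires each toxicity to be classed by its relation to the procedures and to the study drugs.

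**The concern.** By Day 3 these patients have had a stereotactic biopsy, two brain catheters and a lumbar drain, so their CSF may be abnormal before any drug is given. A raised cell count after the dose can point to the procedure or to nivolumab, and without a pre-dose value the reader cannot tell whether it was already raised. Gram stain and culture address infection. They do not separate sterile post-surgical inflammation from a drug effect.

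Relatedness has consequences in this plan. The safety of microdialysis is a primary outcome (9.1), summarised only by frequencies and percentages (10.1), so with 10 completed patients one misassigned case moves a rate by 1/10, or 10 percentage points. Relation to the procedure also enters the Safety Monitoring Committee triggers in 8.1.1 and 14.3. Section 14.3 requires that meeting within 2 weeks and holds enrollment until it takes place. The stored samples cannot inform such a meeting, because 4.5.1 sends samples for cytokine testing only when enrollment has ended.

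**Working it through.** The plan gives no figure for how many patients will have a pre-dose count, so there is nothing to reproduce. The check sets weekdays against study days.

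**Inputs.** Counts on Mondays and Thursdays (8.1.1, 25.0). Surgery on Day 1, dose 48 hours later on Day 3, resection on Day 8, ICU for the first 24 hours (4.5.1). Target of 10 completed patients (3.1). The weekday of surgery is not stated.

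**Step 1: count days by weekday of surgery.**

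| Day 1 falls on | Study days with a count | Count before the Day 3 dose? | Count on Days 4 to 7 |
|---|---|---|---|
| Monday | 1, 4, 8 | Day 1 only, if a sample is sent from the ICU | Day 4 |
| Tuesday | 3, 7 | Only if the Day 3 sample precedes the infusion | Day 7 |
| Wednesday | 2, 6 | Day 2, unless ICU time is excluded and the draw falls within 24 hours of surgery | Day 6 |
| Thursday | 1, 5, 8 | Day 1 only, if a sample is sent from the ICU | Day 5 |
| Friday | 4, 7 | None | Days 4 and 7 |

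The text settles neither open question. Section 8.1.1 speaks of the inpatient unit and the calendar footnote of the inpatient stay, which leaves the ICU day in doubt. The order of the Day 3 safety sample and the infusion is not given. By contrast, the same list in 8.1.1 places liver tests and CPK on Day 3 ahead of the drug.

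**Step 2: expected number without a pre-dose count.** Assume surgeries fall evenly on Monday to Friday. Then the expected number is 10 × (weekdays without a pre-dose count) / 5.

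| Reading | Weekdays without one | Expected of 10 |
|---|---|---|
| Day 1 sample sent; Day 3 sample before the dose | Fri | 10 × 1/5 = 2 |
| Day 1 sample sent; Day 3 sample after the dose | Tue, Fri | 10 × 2/5 = 4 |
| Day 1 sample not sent; Day 3 sample before the dose | Mon, Thu, Fri | 10 × 3/5 = 6 |
| Day 1 sample not sent; Day 3 sample after the dose | Mon, Tue, Thu, Fri | 10 × 4/5 = 8 |

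All four rows treat Wednesday as covered. If the Day 2 draw were also lost to the ICU exclusion, the last two rows would each rise by 2. Spreading surgeries evenly over seven days gives 10 × 1/7 = 1.4 to 10 × 5/7 = 7.1.

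**Step 3: post-dose coverage.** Every weekday gives at least one count on Days 4 to 7. The gap is on the baseline side only.

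**Step 4: after the change.** With a count on the CSF already drawn before the Day 3 dose, 0 of 10 patients lack a baseline by design, provided the drain works.

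**The case against.** The strongest reply is that the Monday and Thursday samples were never meant for attribution. They carry gram stain and culture and last as long as the drain does, which fits surveillance for drain infection, a risk that section 7.15 puts at 4.2 to 5.7%. Twice-weekly sampling is a reasonable choice for that purpose, and that stands. It is why those collections should be kept.

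Second, a baseline would not settle the cause. It would be taken 48 hours after surgery, the catheters and drain stay in until Day 8, and there is no control arm. A later rise could still be evolving procedural inflammation, infection or drug. This also stands: the baseline aids attribution without deciding it.

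Third, some safety actions do not depend on relatedness. Section 14.3 pauses enrollment for any Grade 3 or higher SAE in Phase 1 after the first three patients, whatever its cause. That is true, but relation to the procedure still enters other triggers in 8.1.1 and 14.3, and section 8.2 requires it to be recorded throughout.

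Fourth, CSF immune cells are already an exploratory outcome (9.2, item 5), compared before and after treatment (10.1). However, no counting method is given, and the daily samples are frozen with no count specified.

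A reader might infer that the tally for drug safety is at risk as well. The documents do not support this. The drug-safety primary outcome in 9.1 concerns nivolumab with BMS-986016, and BMS-986016 starts on Day 17, after the drain has come out on Day 8. The aseptic meningitis experience in 7.17.1.2.2 is mainly from the combination (9 of 10 cases), and that section calls the event rare with nivolumab alone.

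**Conclusion.** The point holds in a limited form. Because CSF counts follow the weekday, a count before the first nivolumab dose is not guaranteed. Friday surgery certainly has none; the other weekdays turn on wording that the plan leaves open. Under an assumed even spread over Monday to Friday, with Wednesday treated as covered, about 2 to 8 of 10 patients would lack one. The width of that range comes from the text, and its level depends on surgery weekdays that the documents do not give.

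A reader might go further and infer that most patients will have no baseline, or that a post-dose pleocytosis cannot be attributed at all. Neither follows. Only one weekday in five is certain to lack a pre-dose count, and culture, gram stain, protein, glucose and the clinical picture remain available. What is lost is one piece of evidence, in some patients, for reasons unrelated to the patient. That matters for the microdialysis-safety outcome and the procedure-related review triggers. It is worth correcting because the fluid is already being drawn: the gap lies in which tests are run and not in the sampling.

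**What to change.** Keep the Monday and Thursday collections. Add to section 8.1.1 and to the CSF footnote in 25.0: *In every patient with a working lumbar drain, a cell count with differential, protein and glucose will be run, before freezing, on an aliquot of the CSF already drawn before nivolumab on Day 3. When relatedness of a CSF finding is assessed, later counts will be shown as change from this value.*

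No added Day 7 count is needed, since every surgery weekday already gives a post-dose count on Days 4 to 7.

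The cost is one extra set of routine laboratory tests per patient and a short addition in two places, with no new procedure. Two limits remain. The pre-dose draw must have fluid to spare beyond the pharmacokinetic need, which the documents do not state. And a baseline at 48 hours after surgery aids attribution but does not settle it.

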- 17. Have an active infection that requires systemic antibacterial, antiviral or antifungal therapy < 7 days prior to initiation of study drug therapy
- 18. Have a history of transfer of autologous or allogeneic T cells
- 19. Have a history of solid organ or tissue transplants
- 20. Have cardiac Troponin T or I > 2x the institutional upper limit of normal at screening
- 21. At the time of enrollment, lack of consent capacity due to cognitive impairment that would make them incapable of understanding the explanation of the procedures in this study. Cognitive capacity to consent will be determined at the time of enrollment. Patients with mental disorders or those patients who are cognitively impaired yet still retain consent capacity will not be excluded.
- 22. Cannot speak English or Spanish fluently
- 23. Patients that require dexamethasone > 4 mg/ day or equivalent of steroids

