4.3 Screening Methods

After a patient has signed consent for this protocol, screening will occur, during which patients will have a history and physical exam that may identify unsuspected exclusion criteria. The patient will undergo blood tests, including a troponin, an EKG, a chest X-ray

and an echocardiogram. Study investigators will again review records to attempt to identify exclusion criteria. Screening will also include a blood or urine pregnancy test for women of childbearing age, as pregnant women cannot be enrolled in the protocol. After screening has completed, the patient will be fully enrolled in the trial.

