4.5.3 History, Physical Examination, and Neurological Examination (Research and

Clinical Care)

A credentialed doctor, physician assistant or nurse practitioner who is capable of making an independent determination of the patient's suitability for this trial will take a medical history and perform a physical examination. This clinician will have to be knowledgeable about the study as a whole, particularly the risks of the study interventions and eligibility criteria. This physical examination is for purposes of clinical care only and does not replace any examination the patient may receive from his/her own physicians. For patients who have been referred to the Surgical Neurology Branch as a surgical candidate, this history and physical will be deemed sufficient as part of the evaluation for participation in the trial. If the patient in question is a patient currently being followed by the Surgical Neurology Branch, such that they have not been specifically referred to the Surgical Neurology Branch for surgical resection prior to being identified as a trial participant, the patient's records will be sent to an outside independent neurosurgeon to determine suitability of the patient for repeat surgical resection. The history and physical will be repeated at each visit for Nivolumab and BMS-986016 infusion and monitoring, every two weeks (+/- 2 days).

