4.5.5 Blood drawing (Research and Clinical Care)

Blood will be drawn through a needle in the patient's arm. For adults, blood tests will be drawn prior to MRI to evaluate kidney function (if required per MRI contrast requirements) and before surgery to evaluate serum chemistry, including markers of liver functioning, hematology and coagulation. Up to 35ml of blood will be withdrawn for research purposes at the time of study enrollment. Up to 35ml of blood will also be drawn daily during the immune monitoring period for research including pharmacokinetic analysis after checkpoint inhibition to determine the expression of inflammatory markers and cell content of the blood at these time points. On Day 3, additional samples of up to 10 ml of blood (total on Day 3 up to 45ml) will be drawn. Up to 5ml of blood will be withdrawn before, and 6 hours +/- 2 hours after the completion of the nivolumab dose for pharmacokinetic analysis. Up to 35ml of blood will also be drawn at every 2 week (+/- 2 days) visit for Nivolumab infusion. We will not exceed 550ml in any 8-week period, consistent with existing IRB limits.

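### Five fixed lab limits can bar nivolumab on Day 3, but none is applied before the Day 1 research surgery, and CPK is not drawn until Day 3

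*Combined protocol and SAP*

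**What the plan says.** Section 8.1.1 introduces its dosing bars with "Lab values that would preclude dosing of Nivolumab include". Five are fixed multiples of the upper limit of normal (ULN): AST and ALT above 3.0, total bilirubin above 1.5, WBC above 2.0 and CPK above 2.0. The sixth, creatinine, also requires a rise above 1.5 times the patient's own baseline. It cannot serve as a simple entry limit and is left out of this point.

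On timing, section 4.5.1 puts the biopsy, catheters and lumbar drain on Day 1 and then states: "The first dose of Nivolumab will be given at 48 hours after the biopsy on study day 3".

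Before surgery, section 4.5.5 has blood drawn "before surgery to evaluate serum chemistry, including markers of liver functioning, hematology and coagulation", and the Study Calendar (section 25.0) marks liver function tests and a CBC in the Before Surgery column. Section 4.3 says of screening: "The patient will undergo blood tests, including a troponin, an EKG, a chest X-ray". No limit for the five analytes is given in 3.2, 3.3, 4.3 or section 27.0. For CPK, section 8.1.1 says: "Patients will undergo CPK testing on day 3 prior to study drug administration". The calendar agrees: its CPK row has no mark before Day 3.

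Troponin is handled differently. It is drawn at screening and has an exclusion limit in 3.3: "Have cardiac Troponin T or I > 2x the institutional upper limit of normal at screening".

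**The concern.** The limits decide whether the patient can receive the dose that the microdialysis is there to study, yet they are applied only after the invasive research procedures. Before surgery, an abnormal result could be repeated or the operation postponed. Afterwards the patient has already taken the surgical risk.

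Two things are at stake. One is exposure to a research biopsy, two brain catheters and a lumbar drain in someone who, on information available or obtainable beforehand, could not be dosed on schedule. The other is that patient's interferon-gamma response, the first primary outcome in a trial of 10.

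The protocol also does not say what happens to such a patient. Section 8.6 does not list a barred Day 3 dose, and the replacement rule in 3.1 turns on not completing monitoring and resection, not on a missed dose.

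**Working it through.** **Limits against pre-surgery gates**

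| Analyte | Day 3 bar (8.1.1) | Drawn before surgery? | Limit before surgery? |
|---|---|---|---|
| AST, ALT | > 3.0 × ULN | Yes (4.5.5, 25.0) | None |
| Total bilirubin | > 1.5 × ULN | Yes (25.0) | None |
| WBC | > 2.0 × ULN | Yes (CBC, 25.0) | None |
| CPK | > 2.0 × ULN | No | None |

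The calendar also marks a metabolic panel and CBC on Day 1, without saying whether they come before the operation.

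**Timetable**

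Section 9.1 sets the post-treatment value on the 5th day after nivolumab.

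- Dose on Day 3: 3 + 5 = Day 8, the day of resection and catheter removal.
- Dose one day late: 4 + 5 = Day 9, after the catheters are out.

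Day 17 carries a window of ±2 days. No window is stated for the Day 3 dose or the Day 8 resection.

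**Size**

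The plan gives no figure for how often a patient would be outside a limit before surgery, so there is nothing of its own to reproduce. Assumption: prevalence *p* = 0.005 to 0.02, with *n* = 10 implanted patients.

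- Expected patients implanted and then barred for a reason already present, *np*: 10 × 0.005 = 0.05 to 10 × 0.02 = 0.20.
- Chance of at least one, 1 − (1 − *p*)^10: 1 − 0.995^10 ≈ 0.05 to 1 − 0.98^10 ≈ 0.18.
- Expected symptomatic hemorrhages, using the 1% biopsy risk in 7.9: 0.05 × 0.01 = 0.0005 to 0.20 × 0.01 = 0.002.
- Expected drain infections, using the 4.2% to 5.7% in 7.15: 0.05 × 0.042 = 0.0021 to 0.20 × 0.057 = 0.0114.
- Sum of the two: 0.0026 to 0.0134 expected events.
- Per affected patient: 0.01 + 0.042 = 0.052 to 0.01 + 0.057 = 0.067.

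**The case against.** The strongest reply is that informal gates already exist. Section 3.3 excludes conditions that make surgery unsafe, severe immunodeficiency, known active hepatitis B or C, recent infection needing systemic treatment, and dexamethasone above 4 mg/day. An anesthesiologist sees the patient (7.8), and the examining clinician must know the study, "particularly the risks of the study interventions and eligibility criteria". Inclusion 4 also requires eligibility for protocol 03-N-0164, whose criteria are not in these documents. A markedly raised AST would probably be noticed. This narrows the gap for four of the five analytes, but these gates mainly ask whether surgery is safe, not whether the patient can be dosed on Day 3. None can catch a CPK that has not been drawn.

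Other points carry some weight:

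- **Schedule.** Perfusion is for approximately 7 days (4.5.12), and 7.14 cites microdialysis for up to 10 or 11 days, so a late dose with a late resection is conceivable. The protocol does not provide for it, so loss of the value is likely under the plan as written but not certain.
- **Drain infection rate.** The 4.2% to 5.7% is for prolonged drainage. If the drain came out early in a barred patient, the per-patient sum would be lower. No rule requires early removal in this case.
- **Replacement.** If undosed patients were replaced, the ceiling of 25 leaves 10 dosed patients reachable with probability above 0.999, even if 20% failed a limit. That restores the count but does not undo surgery already done.
- **Where the check belongs.** Pre-operative bloods may be up to 2 weeks old at surgery (4.5.1), so a check just before dosing is right. It should stay, with a gate added ahead of surgery.

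**Conclusion.** The point holds as a minor design weakness. The text is clear on each fact: five fixed limits apply at Day 3, none applies before Day 1, and CPK is not measured before Day 3. Following the plan as written can put a patient through research neurosurgery that then cannot yield the value it was done to obtain.

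The expected size is small: 0.05 to 0.2 patients and about 0.003 to 0.013 events in 10 implanted patients. This rests on an assumed prevalence of 0.5% to 2%, which the documents neither support nor contradict. The 5% to 7% per affected patient uses the protocol's own risk figures and is towards the high side if drains are removed early.

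The loss is limited. The patient still counts for microdialysis safety, and combination dosing from Day 17 remains possible, since 8.1.2 rechecks the same limits then and 8.6 does not make a missed Day 3 dose a reason to stop. The sample-size calculation is not in question.

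**What to change.** 1. Add CPK to the Before Surgery blood draw in 4.5.5 and section 25.0.
2. Add the five 8.1.1 limits (AST, ALT, total bilirubin, WBC, CPK) to 3.3 and section 27.0 as a go/no-go on the most recent result before surgery, allowing a repeat test when an abnormality may be transient.
3. Leave the Day 3 check unchanged, because it catches changes that arise after surgery.

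The cost is one analyte on an existing draw, one eligibility line and one checklist line. A few candidates may be delayed or screened out, which matters somewhat at the expected accrual of 1 to 2 patients per month. Bars that first arise between Day 1 and Day 3 are not prevented.
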